6.4 Concomitant medications

6.4.1 Permitted concomitant therapy

The patient must be told to notify the investigational site about any new medications he/she takes after the start of the study drug. As well as any changes in the dose of any medication the patient was taking prior to or during the study. All medications (other than study drug) and significant non-drug therapies (including physical therapy, herbal/natural medications and blood transfusions) administered during the study must be listed on the Concomitant Medications/Significant Non-Drug Therapies CRF. Note: Concomitant medications information will not be collected for the patients who continue the study treatment beyond 2 years (See Table 7-2). Diabetic patients must continue their treatment for diabetes throughout the study as indicated. If oral contraception is used, the patient must have been practicing this method of birth control for at least two months prior to enrollment and must agree to continue the oral contraceptive throughout the course of the study and for three months after the last dose of study drug.

6.4.2 Permitted concomitant therapy requiring caution and/or action

Investigators should discourage patients from taking any medication during the study, with the exception of medications that are required to treat an adverse event.

6.4.3 Prohibited concomitant therapy

For patients with medication naïve acromegaly or pituitary gigantism the single dose of short acting octreotide or short-acting dopamine agonists should not be administered within 3 days prior to Visit2 (baseline). In case of a single dose of short-acting octreotide, the dose should not be used to predict the response to the octreotide treatment.

The use of the following treatments is prohibited after start of study.

- Other investigational drug or therapy.
- Medication known to affect GH or IGF-1 concentration should not be taken during this study.

The use of concomitant medications with a known risk for QT prolongation is prohibited and requires the discontinuation of the patient from the study prior to starting the respective QT prolonging medication. Please refer to [Appendix 2](#) for guidance regarding medications which pose a known risk for QT prolongation.

6.5 Patient numbering, treatment assignment or randomization

6.5.1 Patient numbering

Each patient is identified in the study by a Patient Number (Patient No.), that is assigned when the patient is first enrolled for screening and is retained as the primary identifier for the patient throughout his/her entire participation in the trial. The Patient No. consists of the Center Number (Center No.) (as assigned by Novartis to the investigative site) with a sequential patient number suffixed to it, so that each Patient is numbered uniquely across the entire database. Upon signing the informed consent form, the patient is assigned to the next sequential Patient No. available to the investigator.

Only the assigned patient number should be entered in the field labeled “Patient number on the EDC data entry screen (e.g. enter ‘1’, ‘2’, etc.). Once assigned, the patient number must not be reused for any other patient and the patient number for that individual must not be changed, even if the patient is re-screened.

6.5.2 Treatment assignment or randomization

6.5.2.1 Randomization number

If the patient is deemed eligible for the study and will commence dosing, a randomization number will be assigned. Once assigned to a subject, a randomization number will not be reused.

Patients who have prior medications will be assigned randomization numbers [REDACTED] and patients who don't have prior medications will be assigned randomization numbers [REDACTED]

Table 6-4 Treatment assignment numbering

| | With prior medication | Without prior medication |
|-----------------------|-----------------------|--------------------------|
| Randomization numbers | [REDACTED] | [REDACTED] |

Patients will be assigned to one of the 3 treatment arms ([Section 4.1](#) and [Section 6.1](#)) in a ratio of 1:1:1.

Randomization will be stratified by prior medications (i.e. somatostatine analogue and dopamine agonist) (yes or no).

Randomization will be performed using the following procedure to ensure that treatment assignment is unbiased. Random permuted blocks scheme will be used for this study.

A randomization list will be produced by or under the responsibility of Novartis Drug Supply Management using a validated system that automates the random assignment of treatment groups to randomization numbers in the specified ratio. The randomization list will be reviewed by a Biostatistics Quality Assurance Group and locked by them after approval.

Prior to dosing, all patients who fulfill all inclusion/exclusion criteria will be assigned the lowest available number on the randomization list.

6.5.3 Treatment blinding

This is an open-label study. However, in order to minimize the potential impact of treatment knowledge, treatment allocation, dose information and PK data will not be accessed by sponsor except data manager and CRA until it will be locked for the primary analysis. The investigators and patients have full knowledge of the treatment allocation.

6.6 Study drug preparation and dispensation

Novartis supplies pasireotide LAR to the investigational sites as 20 mg and 40mg vials. All dosages given to the patient and all dose changes during the study must be recorded on the Dosage Administration Record CRF.

Instructions for Use can be found in [Appendix 1](#).

6.6.1 Study drug packaging and labeling

Pasireotide LAR will be provided as powder for suspension in vials and solution for suspension (“vehicle”) will be provided in ampoules. Medication labels will be in the local language and comply with the legal requirements of Japan. They will include storage conditions for the drug (For details, see study drug handling procedure which is provided by Novartis)

6.6.2 Drug supply and storage

Study treatments must be received by a designated personnel at the study site, handled and stored safely and properly, and kept in a secured location to which only the investigator and designated site personnel have access. Upon receipt, pasireotide LAR should be stored according to the instructions specified on the study drug handling procedure.

For any further information on the formulation, storage and handling of SOM230, please consult the investigators brochure.

6.6.3 Study drug compliance and accountability

6.6.3.1 Study drug compliance

Study drug compliance will be assessed by the Dosage Administration Record. All information is to be noted in the Dosage Administration Record.

6.6.3.2 Study drug accountability

The investigator or designee must maintain an accurate record of the shipment and dispensing of study treatment in a drug accountability log. Drug accountability will be noted by the field monitor during site visits and at the completion of the study.

At study close-out, and, as appropriate during the course of the study, the investigator will return all used and unused study treatment, packaging, drug labels, and a copy of the completed drug accountability log to the Novartis monitor or to the Novartis address provided in the investigator folder at each site.

6.6.3.3 Handling of other study treatment

Not applicable.

6.6.4 Disposal and destruction

The study drug supply can be destroyed at the local Novartis facility, Drug Supply group or third party, as appropriate.

7 Visit schedule and assessments

7.1 Study flow and visit schedule

[figure not shown]
[Table 7-1](#) and [Table 7-2](#) list all of the assessments and indicate with an “X”, the visits when they are performed. All data obtained from these assessments must be supported in the patient’s source documentation. The table indicates which assessments produce data to be entered into the database (D) or remain in source documents only (S) (“Category” column).

The blood sampling schedule at each visit for PK and GH are shown in [Table 7-3](#). Patients are to fast overnight for at least 8 hours prior to all blood samples being taken.

[figure not shown]
No CRF will be used as a source document.

Table 7-1 Visit evaluation schedule (core phase)

| | Category | Reference | Screening | Baseline | | | | | | | | | | | | | | | | End of study treatment Core phase ^D | Study completion |
|---|----------|------------|-----------|----------|---|----|------|----|----|------|----|-----|------|----|----------|-----|----------|-----|----------|--|---------------------------------|
| Visit number | | | 1 | 2 | 3 | 4 | 5 | 6 | 7 | 8 | 9 | 10 | 11 | 12 | 13,14 | 15 | 16,17 | 18 | 19,20 | 777 | 779 |
| Study day | | | -28 to -1 | 1 | 2 | 15 | 22 | 29 | 43 | 50 | 57 | 71 | 78 | 85 | 113, 141 | 169 | 197, 225 | 253 | 281, 309 | 337 | 56 days following the last dose |
| Month (1 month = 28 days) | | | | 0 | | | 0.75 | 1 | | 1.75 | 2 | 2.5 | 2.75 | 3 | 4,5 | 6 | 7,8 | 9 | 10,11 | 12 | 14 |
| pasireotide LAR Injection ^A | D | 6.1 | | 1 | | | | 2 | | | 3 | | | 4 | 5,6 | 7 | 8,9 | 10 | 11,12 | | |
| Informed Consent | D | 11.3 | X | | | | | | | | | | | | | | | | | | |
| Inclusion/Exclusion criteria | S/D | 5.2, 5.3 | X | X | | | | | | | | | | | | | | | | | |
| Relevant Medical history | D | 7.1.1.3 | X | | | | | | | | | | | | | | | | | | |
| History of acromegaly or pituitary gigantism | D | 7.1.1.3 | X | | | | | | | | | | | | | | | | | | |
| Prior therapy for acromegaly or pituitary gigantism | D | 7.1.1.3 | X | | | | | | | | | | | | | | | | | | |
| Archival Tumour Sample | D | 7.2.4.1 | | X | | | | | | | | | | | | | | | | | |
| Demography | D | 7.1.1.3 | X | | | | | | | | | | | | | | | | | | |
| Physical Examination | S | 7.2.2.1 | X | X | | | X | X | | | X | | | X | X | X | X | X | X | X | X |
| Vital signs | D | 7.2.2.2 | X | X | | | X | X | | | X | | | X | X | X | X | X | X | X | X |
| Height | D | 7.2.2.3 | X | | | | | | | | | | | | | | | | | | |
| Weight | D | 7.2.2.3 | X | X | | | X | X | | | X | | | X | X | X | X | X | X | X | X |
| MRI | D | 7.2.1.3 | X | | | | | | | | | | | | | X | | | | X | |
| ECG | D | 7.2.2.5.1 | X | X | | | X | X | | | X | | X | X | X | X | X | X | X | X | X |
| Gallbladder ultrasound | D | 7.2.2.4.10 | X | | | | | | | | | | X | | X | | | X | | X | |
| Hematology | D | 7.2.2.4.1 | X | X | | | X | X | | | X | | | X | X | X | X | X | X | X | X |

| | Category | Reference | Screening | Baseline | | | | | | | | | | | | | | | | End of study treatment Core phase ^D | Study completion | |
|---|---------------------------------------|---------------------------|--------------------------|----------|----------------|----|------|----|----|------|----|-----|----------------|----------------|----------|----------------|----------|-----|----------|--|---------------------------------|---|
| Visit number | | | 1 | 2 | 3 | 4 | 5 | 6 | 7 | 8 | 9 | 10 | 11 | 12 | 13,14 | 15 | 16,17 | 18 | 19,20 | 777 | 779 | |
| Study day | | | -28 to -1 | 1 | 2 | 15 | 22 | 29 | 43 | 50 | 57 | 71 | 78 | 85 | 113, 141 | 169 | 197, 225 | 253 | 281, 309 | 337 | 56 days following the last dose | |
| Month (1 month = 28 days) | | | | 0 | | | 0.75 | 1 | | 1.75 | 2 | 2.5 | 2.75 | 3 | 4,5 | 6 | 7,8 | 9 | 10,11 | 12 | 14 | |
| Coagulation Parameters (PT and APTT) | D | 7.2.2.4.2 | X | X | | | X | X | | X | X | | | X | X | X | X | X | X | X | X | X |
| HbA1c | D | 7.2.2.4.3 | X | X | | | | | | | | | | X | | X | | X | | X | X | X |
| Biochemistry (Including LFTs) | D | 7.2.2.4.3 | X | X | | | X | X | | | X | | | X | X | X | X | X | X | X | X | X |
| Fasting blood glucose | D | 7.2.2.4.3 | X | X | | | X | X | | | X | | | X | X | X | X | X | X | X | X | X |
| Fasting serum cortisol | D | 7.2.2.4.5 | | X | | | | | | | | | | X | | X | | X | | X | X | X |
| Plasma ACTH | D | 7.2.2.4.6 | | X | | | | | | | | | | X | | X | | X | | X | X | X |
| Urinalysis | D | 7.2.2.4.8 | X | X | | | | X | | | X | | | X | X | X | X | X | X | X | X | X |
| Symptoms of Acromegaly or pituitary gigantism | D | 7.2.1.4. | | X | | | | X | | | X | | | X | X | X | X | X | X | X | X | |
| Pregnancy test | D | 7.2.2.4.9 | X | X | | | | X | | | X | | | X | X | X | X | X | X | X | X | X |
| PK Blood collection | D | 7.2.3. | | X | | | X | X | | | X | X | X | X | X | X | X | X | X | X | X | |
| Efficacy assessments | GH profile | D | 7.2.1.1. | X | X | | | | | | | | X | X | | X | | X | | X | | |
| | PRL | D | 7.2.1.5. | X | X | | | | | | | | X | | | X | | X | | X | | |
| | IGF-1 | D | 7.2.1.2. | X | X | | | | | | | | X | X | | X | | X | | X | | |
| | GH suppression post OGTT ^B | D | | X | | | | | | | | | | | | | | | | | | |
| PD assessment | GH | D | 7.2.3 | | X | | X | X | | | X | X | X | X | X | X | | | | | | |
| | IGF-1 | D | 7.2.3 | | X ^C | | X | X | | | X | X | X ^C | X ^C | X | X ^C | | | | | | |

| | Category | Reference | Screening | Baseline | | | | | | | | | | | | | | | End of study treatment Core phase ^D | Study completion | |
|---|----------|---------------------------|------------------|----------|----------|-----------|-----------|-----------|-----------|-----------|-----------|-----------|-----------|-----------|-----------------|------------|-----------------|------------|--|------------------|--|
| Visit number | | | 1 | 2 | 3 | 4 | 5 | 6 | 7 | 8 | 9 | 10 | 11 | 12 | 13,14 | 15 | 16,17 | 18 | 19,20 | 777 | 779 |
| Study day | | | -28 to -1 | 1 | 2 | 15 | 22 | 29 | 43 | 50 | 57 | 71 | 78 | 85 | 113, 141 | 169 | 197, 225 | 253 | 281, 309 | 337 | 56 days following the last dose |
| Month (1 month = 28 days) | | | | 0 | | | 0.75 | 1 | | 1.75 | 2 | 2.5 | 2.75 | 3 | 4,5 | 6 | 7,8 | 9 | 10,11 | 12 | 14 |
| Free T4, TSH | D | 7.2.2.4.7 | X | X | | | | | | | | | | X | | X | | X | | X | X |
| Liver function test | D | 7.2.2.4.4 | | | | | | | | X | | | | | | | | | | | |
| HBsAg and AntiHCV | D | 7.2.2.4.4 | X | | | | | | | | | | | | | | | | | | |
| Study completion data | D | 7.1.3 | | | | | | | | | | | | | | | | | | X | X |
| Adverse events | D | 8.1, 8.3. | CONTINUOUS | | | | | | | | | | | | | | | | | | |
| Concomitant med | D | 6.4. | CONTINUOUS | | | | | | | | | | | | | | | | | | |
| Comments | D | | CONTINUOUS | | | | | | | | | | | | | | | | | | |
| 
A. pasireotide LAR injection and study visits every 28 days +/- 2 days.
 
B Patients' GH nadir within 2 hours after an oral glucose load with 75 g of glucose (OGTT) will be measured. The scheduled time points are at t0, oral glucose, t30, t60, t90, t120 (except for diabetic patients).
 
C Blood sampling of IGF-1 for PD assessment combines with efficacy assessment.
 
D For patients accepting to continue in the extension phase, at 12 months, a 13th injection of the same study treatment received in the core phase will be administered. Patients continuing the study treatment with pasireotide LAR in the extension phase will have the option of receiving pasireotide therapy as long as they do not fulfill any of the study discontinuation criteria or until pasireotide LAR is commercially available or until the pasireotide LAR development program is discontinued (whichever comes first).
 
Visit 21 and Visit 777 are on the same day for patients willing to continue in the extension phase.
 | | | | | | | | | | | | | | | | | | | | | |

[figure not shown]
[figure not shown]

Table 7-2 Extension Visit evaluation schedule

| | Category | Reference | | | | | | | | | | | | | | | | End of study treatment for Ext | Study completion |
|--|----------|------------|-----|-----|-----|-----|-----|-----|-----|-----|-----|-----|-----|-----|-----|-------------------------|-----|---------------------------------|------------------|
| Visit number | | | 21 | 22 | 23 | 24 | 25 | 26 | 27 | 28 | 29 | 30 | 31 | 32 | 33 | 34 and following visits | 778 | 779 | |
| Study day | | | 337 | 365 | 393 | 421 | 449 | 477 | 505 | 533 | 561 | 589 | 617 | 645 | 673 | 701, 729, 757, 813... | | 56 days following the last dose | |
| Month (1 month = 28 days) | | | 12 | 13 | 14 | 15 | 16 | 17 | 18 | 19 | 20 | 21 | 22 | 23 | 24 | 25- | | | |
| pasireotide LAR Injection ^A | D | 6.1 | 13 | 14 | 15 | 16 | 17 | 18 | 19 | 20 | 21 | 22 | 23 | 24 | 25 | 26- | | | |
| Physical Examination | S | 7.2.2.1 | | X | X | X | X | X | X | X | X | X | X | X | X | | X | X | |
| Vital signs | D | 7.2.2.2 | | X | X | X | X | X | X | X | X | X | X | X | X | | X | X | |
| Weight | D | 7.2.2.3 | | X | X | X | X | X | X | X | X | X | X | X | X | | X | X | |
| ECG | D | 7.2.2.5.1 | | | | X | | | X | | | X | | | X | | X | X | |
| Gallbladder ultrasound | D | 7.2.2.4.10 | | | | X | | | X | | | X | | | X | | X | | |
| Hematology | D | 7.2.2.4.1 | | | | X | | | X | | | X | | | X | | X | X | |
| Coagulation Parameters (PT and APTT) | D | 7.2.2.4.2 | | | | X | | | X | | | X | | | X | | X | X | |
| HbA1c | D | 7.2.2.4.3 | | | | X | | | X | | | X | | | X | | X | X | |
| Biochemistry | D | 7.2.2.4.3 | | | | X | | | X | | | X | | | X | | X | X | |
| Fasting blood glucose | D | 7.2.2.4.3 | | X | X | X | X | X | X | X | X | X | X | X | X | | X | X | |
| Fasting serum cortisol | D | 7.2.2.4.5 | | | | X | | | X | | | X | | | X | | X | X | |
| Plasma ACTH | D | 7.2.2.4.6 | | | | X | | | X | | | X | | | X | | X | X | |
| Urinalysis | D | 7.2.2.4.8 | | | | X | | | X | | | X | | | X | | X | X | |
| Pregnancy test | D/S | 7.2.2.4.9 | | X | X | X | X | X | X | X | X | X | X | X | X | X | X | X | |

| | Category | Reference | | | | | | | | | | | | | | | End of study treatment for Ext | Study completion |
|--|------------|-----------|------------------------------|-----|-----|-----|-----|-----|-----|-----|-----|-----|-----|-----|-----|-------------------------|--------------------------------|---------------------------------|
| Visit number | | | 21 | 22 | 23 | 24 | 25 | 26 | 27 | 28 | 29 | 30 | 31 | 32 | 33 | 34 and following visits | 778 | 779 |
| Study day | | | 337 | 365 | 393 | 421 | 449 | 477 | 505 | 533 | 561 | 589 | 617 | 645 | 673 | 701, 729, 757, 813... | | 56 days following the last dose |
| Month (1 month = 28 days) | | | 12 | 13 | 14 | 15 | 16 | 17 | 18 | 19 | 20 | 21 | 22 | 23 | 24 | 25- | | |
| Symptoms of Acromegaly or pituitary gigantism | D | 7.2.1.4 | | | | | | | X | | | | | | X | | X | |
| Efficacy assessments | GH profile | D | 7.2.1.1 | | | | | | X | | | | | | X | | X | |
| | PRL | D | 7.2.1.5 | | | | | | X | | | | | | X | | X | |
| | IGF-1 | D | 7.2.1.2 | | | | | | X | | | | | | X | | X | |
| Free T4, TSH | D | 7.2.2.4.7 | | | | X | | X | | | X | | | X | | X | X | |
| Liver function test | D | 7.2.2.4.4 | | | | X | | X | | | X | | | X | | X | X | |
| Study completion data | | | | | | | | | | | | | | | X | | X* | X* |
| Adverse events | D | 8.1, 8.3 | CONTINUOUS* | | | | | | | | | | | | | | | |
| Concomitant med | D | 6.4 | CONTINUOUS (up to 24 months) | | | | | | | | | | | | | | | |
| Comments | D | | CONTINUOUS* | | | | | | | | | | | | | | | |
| A. pasireotide LAR injection and study visits every 28 days +/- 2 days study treatment | | | | | | | | | | | | | | | | | | |

[figure not shown]

Table 7-3 Blood sampling schedule

| | -120 min | -90 min | -60 min | -30 min | 0 min | 120 min |
|-----------------------------------|---------------------|--------------------|--------------------|--------------------|------------------|--------------------|
| PK (Day 1,) | | | | | X | X |
| PK (except for Day 1) | | | | | X | |
| GH (Day 1, 85) | X | X | X | X | X | X |
| GH (Scr, Day 78, 169, 253, 337) | X | X | X | X | X | |
| GH (Day 22, 29, 57, 71, 113, 141) | | | | | X | |

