7.2.1.5 Prolactin (PRL)

PRL levels will be assessed at visits indicated in [Table 7-1](#) and [Table 7-2](#). T0 is defined as time point immediately pre-dose with respect to pasireotide LAR injection. The samples for PRL will be analyzed by the central laboratory, [REDACTED]. Please refer to the [REDACTED] [REDACTED] for processing details.

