7.2.3 Pharmacokinetics

To assess the pharmacokinetic profile of pasireotide administered as LAR, blood samples will be collected at the predefined time points ([Table 7-5](#)) and plasma concentration of pasireotide will be measured. The time of blood collection will be recorded on the PK blood collection eCRF page.

Descriptive statistics and graphical depiction (mean and individual) for pasireotide plasma concentrations during the course of treatment will be performed.

[figure not shown]

Table 7-5 Blood sampling for PK assessment

| Sample | Volume (mL) | Visit | Week | Day | PK Collection number | Sample number | Scheduled time (hr) |
|--------|-------------|-------|------|-----|----------------------|-------------------|-------------------------------|
| Blood | 2.5 | 2 | 0 | 1 | 1 | 1 | 0 (pre-dose) |
| Blood | 2.5 | 2 | 0 | 1 | 1 | 2 | 2 |
| Blood | 2.5 | 5 | 3 | 22 | 1 | 6 | 504 |
| Blood | 2.5 | 6 | 4 | 29 | 2 | 7 | 672/0 (pre-dose) ¹ |
| Blood | 2.5 | 9 | 8 | 57 | 3 | 9 | 672/0 (pre-dose) ¹ |
| Blood | 2.5 | 10 | 10 | 71 | 3 | 10 | 336 |
| Blood | 2.5 | 11 | 11 | 78 | 3 | 11 | 504 |
| Blood | 2.5 | 12 | 12 | 85 | 3, 4 | 12 | 672/0 (pre-dose) ¹ |
| Blood | 2.5 | 13 | 16 | 113 | 5 | 13 | 0 (pre-dose) |
| Blood | 2.5 | 14 | 20 | 141 | 6 | 14 | 0 (pre-dose) |
| Blood | 2.5 | 15 | 24 | 169 | 7 | 15 | 0 (pre-dose) |
| Blood | 2.5 | 16 | 28 | 197 | 8 | 16 | 0 (pre-dose) |
| Blood | 2.5 | 17 | 32 | 225 | 9 | 17 | 0 (pre-dose) |
| Blood | 2.5 | 18 | 36 | 253 | 10 | 18 | 0 (pre-dose) |
| Blood | 2.5 | 19 | 40 | 281 | 11 | 19 | 0 (pre-dose) |
| Blood | 2.5 | 20 | 44 | 309 | 12 | 20 | 0 (pre-dose) |
| Blood | 2.5 | 777 | 48 | 337 | 12 | 21 | 672 ² |
| Blood | 2.5 | NA | NA | NA | NA | 1001 ³ | Unscheduled |

1 : These samples are treated as samples for 672 hours post dose and pre-dose samples as well.
 2 : The sample must be obtained before pasireotide LAR administration if the subject is enrolled in the extension phase
 3 : Unscheduled blood samples must be uniquely and sequentially numbered from 1001, eq., 1001, 1002...

[figure not shown]

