10.5.1 Key secondary objective(s)

Table 10-1 shows the primary, key secondary and secondary variables for core phase by time point. Table 10-2 shows the secondary variables for extension phase by time point. For the detailed key secondary objectives and secondary objectives, please refer to Table 3-1.

For other key secondary objectives, please refer to Section 10.5.3 (safety and tolerability) and Section 10.5.4 (PK).

Table 10-1 Primary and secondary variables for core phase

| Variables | 3M | 6M | 9M | 12M |
|---|---------------------------------------|-----------------|-----------------|-----------------|
| Proportion of patients with the reduction of mean GH levels to < 2.5µg/L and the normalization of IGF-1 | P (total-group) KS (by dose level) | S (total-group) | S (total-group) | S (total-group) |
| Proportion of patients with the reduction of mean GH levels to < 2.5µg/L | KS (total-group and by dose group) | S (total-group) | S (total-group) | S (total-group) |
| Proportion of patients with the normalization of IGF-1 | KS (total-group and by dose group) | S (total-group) | S (total-group) | S (total-group) |
| Change of tumor volume from baseline | | S | | S |
| Change of mean GH level from baseline | S | | | |
| Symptoms of acromegaly | S | | | |
| Change of PRL level from baseline | S | | | |

P: primary endpoint, KS: key secondary endpoint, S: secondary endpoint

Table 10-2 Primary and secondary variables for core phase

| Variables | 15M | 18M | 21M | 24M |
|---|-----|-----|-----|-----|
| Proportion of patients with the reduction of mean GH levels to < 2.5µg/L and the normalization of IGF-1 | | S | | S |
| Proportion of patients with the reduction of mean GH levels to < 2.5µg/L | | S | | S |
| Proportion of patients with the normalization of IGF-1 | | S | | S |
| Change of mean GH level from baseline | S | | | |

S: secondary endpoint

The response rate at 3 months of study treatment along with the corresponding exact 95% confidence interval will be provided by dose level at randomization study treatment.

For patients with the reduction of mean GH levels to $< 2.5 \mu\text{g/L}$ and patients with the normalization of IGF-1 at 3 months of study treatment, total-group proportions of patients along with the corresponding Clopper-Pearson exact two-sided 95% confidence interval will be provided. The same analyses will be performed by dose level at randomization study treatment.

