5.9.2.2 Other secondary analyses

Other secondary analyses for core phase

Most secondary objectives were reported in [the 12 months CSR] and not applicable in this document. The below analyses, which were previously performed, will be repeated with updated data for the final analysis (most likely at 18 months and 24 months of study treatment).

Proportions of overall patients with the reduction of mean GH levels to < 2.5 ug/L and normalization of IGF-1 will be updated along with subgroup analysis of SSA uncontrolled status, while SSA uncontrolled population is defined as patients who were pre-treated with SSA for >= 12 weeks and patients who were pre-treated with SSA for < 12 weeks or were not pre-treated with SSA are considered as others. Proportions of patients with the reduction of mean GH level to < 2.5 ug/L by visit and with normalization of IGF-1 by visit will be updated along with subgroup analysis of SSA uncontrolled status, respectively.

Bar charts for all total group response rate, proportion of patients with reduction of mean GH level to < 2.5 ug/L and proportion of patients with normalization of IGF-1 will be repeated by visit for updated data.

Total group response rate with over responder by visit will be also updated where over responder is defined as a patient with reduction of mean GH levels to <2.5 ug/L and IGF-1 reached lower than lower limit normal. This summary will be updated with SSA uncontrolled status subgroups as well.

Changes from baseline in mean GH and in normalization of IGF-1 will be updated by visit and SSA uncontrolled status, respectively, in addition to change from baseline in ring size and PRL.

Plots of individual patient absolute value of mean GH and IGF-1 will be re-ran as well.

Changes of tumor volume at 6 and 12 months of study treatment from baseline were reported in [the 12 month CSR] and not applicable in this document. The summary will be repeated by subgroup of categorical longest diameter with 10 mm cut-off in the final analysis. Changes and percent changes will be plotted along with the longest diameter as well.

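### The only on-treatment prolactin sample up to Month 3 is taken 21 days after injection, while all later scheduled samples are 28-day troughs, so Month 3 and later changes are not comparable

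*Protocol*

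**What the plan says.** In Table 7-1 (core phase) the prolactin row begins "PRL | D | 7.2.1.5. | X | X". Its marks are at screening, Day 1, Visit 11 (Day 78), Visit 15 (Day 169), Visit 18 (Day 253) and Visit 777 (Day 337). The GH profile and IGF-1 rows have the same marks plus one at Visit 12 (Day 85). Table 7-2 adds prolactin at Months 18 and 24 (Days 505 and 673), both injection visits.

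Section 7.2.1.5 fixes the prolactin time point: "T0 is defined as time point immediately pre-dose with respect to pasireotide LAR injection". Table 7-1 lists no injection at Visit 11.

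Change in prolactin is a secondary endpoint. Table 10-1 has "Change of PRL level from baseline | S", with the S printed in the 3M column, although the cell may span all columns. Protocol Section 10.5 summarises secondary endpoints by dose level and total group up to Month 3, and by total group only afterwards. SAP Section 5.9.2.2 updates GH and IGF-1 changes by visit, "in addition to change from baseline in ring size and PRL". SAP Section 4.1.10 says which GH and IGF-1 value represents a month and gives a window for MRI. It has no rule for prolactin.

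**The concern.** A series of changes from baseline can be read as a time course only if each point is taken at the same place in the dosing interval. Here the first on-treatment prolactin value is taken near the concentration peak and the rest at trough. A difference between Month 3 and Month 6 could then reflect sampling time, the drug's effect over time, or the dose increases allowed from Day 85, and the summary cannot separate them.

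GH and IGF-1 do not have this problem to the same degree. They are also sampled at Day 85, and SAP Section 4.1.10 takes the last value in the window. Prolactin has no Day 85 sample to fall back on, and every by-dose prolactin summary on treatment rests on the Day 78 value. The documents give no reason for the choice: the Day 78 GH and IGF-1 values feed the Month 3 titration decision in Section 6.3.1, but prolactin plays no part in it. Cortisol, ACTH, free T4, TSH and HbA1c are marked at Visit 12 and not at Visit 11.

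**Working it through.** **1. Which visit the mark belongs to.** In the text available, the efficacy rows of Table 7-1 are slightly out of line with the header, so the reading needs anchors. Table 7-3 lists full GH profiles on Day 1 and Day 85, and separately "GH (Scr, Day 78, 169, 253, 337". Section 6.3.1 names Visit 11 (Month 2.75) as a GH and IGF-1 assessment. The two adjacent on-treatment GH marks are therefore Visits 11 and 12. The prolactin row has the first of these and not the second.

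**2. Time since injection.** Hours = (visit day − last injection day) × 24, with injections every 28 days from Day 1.

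| Visit day | Last injection day | Hours | Injection that day |
|---|---|---|---|
| 78 | 57 | 504 | no |
| 85 (no prolactin) | 57 | 672 | yes, sample pre-dose |
| 169 | 141 | 672 | yes, sample pre-dose |
| 253 | 225 | 672 | yes, sample pre-dose |
| 337 | 309 | 672 | only if entering the extension; sample before it |
| 505 | 477 | 672 | yes, sample pre-dose |
| 673 | 645 | 672 | yes, sample pre-dose |

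This reproduces Table 7-5 for the core-phase PK samples: "Blood | 2.5 | 11 | 11 | 78 | 3 | 11 | 504" for Day 78, "85 | 3, 4 | 12 | 672/0 (pre-dose" for Day 85 and "15 | 24 | 169 | 7 | 15 | 0 (pre-dose" for Day 169.

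**3. Closeness to the peak.** Table 1-2 gives median Tmax,p2 of 456, 480 and 504 h for 20, 40 and 60 mg. Day 78 is 48, 24 and 0 h after these medians.

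**4. Exposure gap at unchanged dose.** Trough/Day 78 ratio = exp(−ln 2 × 168 / t½), with the mean half-lives in Table 1-2. This assumes terminal decline from 504 h; under superposition the ratio is then the same at steady state.

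| Dose | t½ (h) | Trough/Day 78 | Day 78 above trough |
|---|---|---|---|
| 20 mg | 442.9 | 0.77 | 30% |
| 40 mg | 341.3 | 0.71 | 41% |
| 60 mg | 378.3 | 0.74 | 36% |

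**5. Allowing for up-titration from Day 85.** Assume dose-proportional exposure, equal arms, the half-life of the starting dose, and up-titration of every non-responder at the 20 and 40 mg response rates quoted in the sample-size section (30% and 41.7%).

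- 20 mg: 0.769 × (0.70 × 2 + 0.30) = 1.31
- 40 mg: 0.711 × (0.583 × 1.5 + 0.417) = 0.92
- 60 mg: 0.735, with no increase possible
- Mean Day 169/Day 78 ratio: (1.307 + 0.918 + 0.735)/3 = 0.99

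With no up-titration the mean is (0.769 + 0.711 + 0.735)/3 = 0.74. With all 20 and 40 mg patients up-titrated it is (1.538 + 1.066 + 0.735)/3 = 1.11.

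**The case against.** A reader might infer that the total-group summary will show a false loss of effect after Month 3, or that any such fall must be an artefact. The documents do not support that. Trough exposure in a patient moved from 20 to 40 mg is about 1.54 times that patient's Day 78 exposure, and from 40 to 60 mg about 1.07 times. In the total group these increases can cancel the timing gap. A reader might also put the gap as high as 49%. That needs the 10 mg half-life of 290.6 h (ratio 0.67, and 1/0.67 = 1.49), and 10 mg is not a dose in this trial.

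Other objections stand in part:

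- The documents give no relation between pasireotide concentration and prolactin, so an exposure gap cannot be turned into a prolactin bias.
- The half-lives and peak times come from single doses in healthy volunteers. The 60 mg peak ranged from 240 to 576 h, so log-linear decline from 504 h is an approximation.
- Sections 7.2.1.1 and 7.2.1.2 use similar pre-dose wording for GH and IGF-1, which are also drawn on Day 78. The misfit is not unique to prolactin, but only prolactin lacks the Day 85 sample that meets the wording.
- A by-visit table keeps Day 78 on its own row and pools nothing. The rows would still be read as one series.
- Early-discontinuation visits may fall anywhere in the interval, so only the scheduled later samples are all troughs.
- Prolactin is only summarised, with no test or decision attached.
- Enrolment was complete by 31 May 2014 and the Month 12 report is dated 1 July 2015, so the samples exist. The analysis plan for that report is not among the documents, so its labelling cannot be judged.

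**Conclusion.** The point holds as a limited one. The schedule puts the Month 3 prolactin value at a different place in the dosing interval from every later scheduled value. It does not fit the protocol's own pre-dose definition, and neither document resolves this. At unchanged dose the exposure difference is about 30-41%, if single-dose healthy-volunteer half-lives apply.

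The comparison of Month 3 with later visits is therefore confounded, but its direction in the total group is uncertain (Day 169/Day 78 exposure ratio about 0.99, range 0.74 to 1.11 under the assumptions shown). A false loss of effect is possible in patients kept on the same dose, and a gain from up-titration may be masked in others. What is at stake is the reading of one descriptive secondary endpoint; the primary endpoint is unaffected.

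**What to change.** In Table 7-1, move the prolactin mark from Visit 11 to Visit 12 (pre-dose, Day 85). Fasting blood is already drawn at Visit 12, so this adds no visit and no draw. It also reconciles the table with Section 7.2.1.5 and gives prolactin the same 672 h timing at Month 3 as later.

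For samples already taken, add a short rule to the SAP: present the value as Month 2.75 (Day 78, 21 days post-dose), keep it in the report but apart from the trough series that starts at Month 6, and do not interpret the change from it to Month 6 as a change in effect. The cost is one table label and a sentence or two of text.
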